Although considered a modifiable risk factor for coronary artery disease (CAD) in the general population, the magnitude of physical activity required to promote cardiorespiratory fitness and a clinically meaningful change in blood-derived biomarkers of CAD is not achievable in those with a severe physical disability, such as with immobilizing paralysis from spinal cord injury (SCI). During the chronic phase of SCI, a characteristic dyslipidemia emerges, with mean serum high density lipoprotein cholesterol (HDL-C) concentrations <40 mg/dl, a threshold level for HDL-C that is appreciated to be an independent risk factor for CAD, elevations in triglycerides (TG) to concentrations at, or near, target values for the general population that trigger clinical intervention, and low density lipoprotein cholesterol (LDL-C) concentrations that are within the normal range. It should not be a surprise that cardiovascular disease (CVD)-related morbidity in persons with SCI occurs earlier in life, at a greater prevalence than that of the general population, and is the primary cause of death after the first year of injury. Population-based epidemiological studies are unavailable for clinical guidance because of the relatively low incidence rates for SCI. Clinical target values used to initiate treatment in the general population may be inappropriate in those with SCI because of their unique pathophysiology. In the absence of significant physical activity and lifestyle modifications, it would seem that appropriate pharmaceutical options are needed to properly manage markers of CVD-related risk in persons with SCI. To date, there is limited empirical evidence to support the use of lipid-lowering treatments in persons with SCI.

Fenofibrate is a fibric acid derivate that activates peroxisome proliferator-activated receptor α and lipoprotein lipase, leading to enhanced elimination of TG from plasma. In clinical trials where fenofibrate was used as a monotherapy, serum TG concentrations fell 41-53%, very low-density lipoprotein (VLDL) fell 38-52%, LDL-C decreased 6-20%, and HDL-C improved by as much as 20%. In consideration for the nature of dyslipidemia in persons with

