SCI, fenofibrate appears to be an appropriate first-line agent for treatment in this cohort, especially because most of those with SCI have LDL values that are within the clinically acceptable range. In the general population, standard clinical practice for lipid-lowering treatment with fenofibrate monotherapy follows a known and clinically accepted timeline to monitor safety and to determine therapeutic efficacy. It is recommended that, if after 2 months of continuous therapy there are no beneficial changes to the lipoprotein profile, that treatment be discontinued (i.e., non-responders). Similarly, several large clinical trials have demonstrated that the peak therapeutic effects of fenofibrate are observed after 12-16 weeks of treatment (i.e., responders). The proposed study will test the efficacy of administering fenofibrate to persons with SCI, a severely immobilized cohort that does not have established clinical practice guidelines to treat dyslipidemia and appears to have unique considerations that may be hypothesized to call for a more disease-specific approach for care. If successful, the treatment will reduce clinical markers of CVD-related risk by modifying the concentration and number of particles that are known to contribute to incident cardiac events and mortality. It is anticipated that the insight gained from this investigation will provide clinicians with a proof-of-concept for instituting appropriate use of lipid lowering agents to treat the dyslipidemia that has been well described in persons with SCI.

Goals and Objectives

In individuals with spinal cord injury (SCI):

Primary Aim:

1. To determine the efficacy of fenofibrate monotherapy after 2 months of treatment to improve the lipoprotein profile; a successful response will be defined as a 25% reduction in the serum TG concentration at 2 months. This approach will permit the determination of the percent of subjects who show drug efficacy (i.e., responders) versus those who are non-responders after 2 months of treatment, when drug administration will be discontinued if therapeutic efficacy is deemed suboptimal.
2. To determine the efficacy of fenofibrate monotherapy to lower TG concentration at 4 months of treatment, when the peak therapeutic efficacy to drug treatment has been reported to occur. Lipid profiles will be performed in the drug responder and control groups.

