Secondary Aim: To describe the effects of fenofibrate monotherapy on lipoprotein particle number and size by nuclear magnetic resonance spectroscopy performed in non-responders and responders at 2 months of treatment, when drug treatment will be discontinued for lack of efficacy to agent. Lipids in responders and control groups will be studied by NMR spectroscopy at 4 months of treatment, which will be at the termination of the proposed treatment period.

Tertiary Aim: To determine the safety of fenofibrate monotherapy. Documentation and description of adverse events will be obtained in subjects who have received drug treatment compared to events occurring in the control group.

Target Population

It is estimated that approximately 100 participants with SCI will be screened to identify 30 eligible and appropriate SCI participants (i.e., 20 treatment, 10 control) who will agree to participate in the study (Screening data from BAU-11-075 will be used to minimize the number of procedures performed, if it is not older than 45 days). To be considered eligible for the study, participants must meet the following eligibility criteria:

Inclusion Criteria:

- (1) Male or female, age 21 to 69;
- (2) Chronic (e.g., duration of injury at least 6 months), stable SCI (regardless of level of neurological lesion);
- (3) American Spinal Injury Association Impairment Scale (AIS) designation of A, B or C; and
- (4) TG concentration ≥ 135 mg/dl (paraplegia) or ≥ 115 mg/dl (tetraplegia).

Exclusion Criteria (These exclusion criteria were carefully chosen to minimize subject risk and/or confounding factors that are known to affect study endpoints):

- (1) Acute illness or infection;
- (2) Reduced kidney function (by glomerular filtration rate (GFR < 60 ml/min) or liver function tests (LFTs ≥ 2.5 times above the upper limit of normal) as determined by test results at screening and any time point of the study;
- (3) Current pharmacological treatment with: HMG-CoA reductase inhibitors (statins), or any other hypolipidemic agent; anti-coagulant therapy; cyclosporine; or any other medications known to effect the TG concentration (i.e., β -blockers, thiazides or estrogen);
- (4) Hypersensitivity to fenofibrate;
- (5) Existing diagnosis of atherosclerosis, congestive heart failure, or recent history of myocardial infarction (i.e., ≤ 12 months);
- (6) Pregnancy or women who may become pregnant during the course of the study, or those who are nursing;

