The proposed investigation is an open-label, parallel-group intervention and randomized trial to determine the safety and efficacy of fenofibrate monotherapy on the lipoprotein profile in persons with SCI. A screening visit will be performed in up to 100 persons with SCI to identify 30 subjects who have adverse TG concentrations (i.e., paraplegia: ≥ 135 mg/dl; tetraplegia ≥ 115 mg/dl). After a baseline evaluation, a comprehensive medical history review and intake interview will be performed to identify demographic information, current health status, medications and lifestyle habits (i.e., smoking, alcohol consumption, recreational drug use, physical activity habits, diet etc.). Twenty subjects with adverse TG concentrations will be randomized to receive once daily fenofibrate therapy (i.e., 145 mg) for 4 months (dispensed by the research pharmacy of the James J. Peters VA Medical Center) and the remaining 10 subjects with adverse TG concentrations will receive no treatment and will serve as control subjects. All subjects will complete monthly follow-up visits for the study period, which also includes a 1-month post-treatment visit. If after 2 months of continuous fenofibrate treatment a subject does not demonstrate an improvement of $\geq 25\%$ in TG concentration, then he/she will be discontinued from the study drug under appropriate supervision and terminated from the study. For those who respond to fenofibrate treatment, he/she will continue on treatment for an additional 2 months.

The primary study outcome will be to determine the efficacy of treatment on the serum lipoprotein profile (i.e., TG, HDL-C, LDL-C, total cholesterol), and the secondary study

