Additional Outcomes: To assist in the stratification of interventional outcomes, all participants who enter the study intervention (i.e., receive drug or serve as control), will provide a blood sample at the beginning of the treatment period so that their apolipoprotein E (ApoE) genotype can be determined by a commercial laboratory as a fee-for-service procedure (LabCorp). Venous blood samples will be obtained after an overnight fast (minimum 8 hours) for the determination of fasting plasma insulin level and serum glucose concentration at each study visit once the trial begins. For the oral glucose tolerance test, the participant will drink a glucose containing solution (i.e., 75 grams) over a 2-minute period. Venous blood will be drawn from a catheter at time 0 (same blood sample just described) and 120 minutes later to determine plasma glucose and insulin levels. These outcomes will be monitored for changes in glucose tolerance and insulin sensitivity that may be associated with fenofibrate treatment. The Core Laboratory of the Center of Excellence for the Medical Consequences of SCI will perform the glucose analyses (YSI 2300 STAT Plus, YSI Life Sciences, Yellow Springs, OH) and insulin assay by batch processing in duplicate by radioimmunoassay using techniques previously developed by our laboratory.⁵⁸ For body composition analysis, subjects will be transferred from their wheelchair to a semi-padded scanner bed, where a DXA total body scan will be performed. To determine fat mass and fat-free mass, the scan will expose subjects to a very low dose of radiation (i.e., approximately 1/5th of the radiation for a standard chest x-ray). The scan will take no more than 20 minutes to be performed and will only be performed twice during the study (Table 2). Skinfold and Girth Circumference Measurements: a soft measuring tape will be used to measure various circumferences and lengths of each subject's body, and a

set of skin calipers will be used to measure skin folds specifically located on the subject's arms, legs, back, and trunk. The total time of this procedure will not exceed 10 minutes.

Potential Risks

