Separate analysis of variance (ANOVA) will be performed to identify group differences (i.e., control, treatment) for baseline demographic data [e.g., age, height, weight, BMI, duration of injury (DOI)]. Pearson chi-square tests will be performed to identify differences for the number of enrolled participants in each group based on gender (e.g., male, female), injury level (e.g., paraplegia, tetraplegia), AIS level (e.g., A, B, C), and ethnicity (e.g., African American, White, Hispanic). Separate 2 (group: treatment, control) X 3 (visit: baseline, Mo2, Mo4) mixed-model repeated measures ANOVA (RMANOVA) will be performed to determine if differences were present for serum lipoprotein profile [e.g., HDL-C, LDL-C, VLDL-C, TG, TC], glucose, insulin, and the TG/HDL-C, LDL-C/HDL-C and TC/HDL-C ratios. Separate

factorial ANOVA will be performed to identify the presence of group differences in the percent change from baseline to 2 and 4 months, respectively in the serum TG, HDL-C, and LDL-C. The nature of significant group or time main effects will be explored with Tukey *post hoc* tests. Although not part of the primary analysis, results from the venous blood samples at months 1 and 3 visits will be provided. Statistical analyses will be completed using IBM SPSS Statistics 25 (IBM, Armonk, NY) and figures will be created with GraphPad Prism (version 8.0 for Windows, GraphPad Software, San Diego, CA). An *a priori* level of significance was set at $p \leq 0.05$.

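### The 2 x 3 repeated-measures ANOVA counts baseline as a visit without naming the treatment contrast, and no planned group comparison adjusts for the baseline value

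*Combined protocol and SAP*

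**What the plan says.** Three sentences of the Statistical Analyses section bear on this.

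- The main model is a "2 (group: treatment, control) X 3 (visit: baseline, Mo2, Mo4) mixed-model repeated measures ANOVA (RMANOVA) will be performed to determine if differences were present". It covers five lipid measures (HDL-C, LDL-C, VLDL-C, TG, total cholesterol), glucose, insulin and three lipid ratios, ten outcomes in all. Baseline is one of the three levels of the visit factor.
- A separate "factorial ANOVA will be performed to identify the presence of group differences in the percent change from baseline to 2 and 4 months". This covers TG, HDL-C and LDL-C only, and no covariate is stated.
- The follow-up rule comes after both: "The nature of significant group or time main effects will be explored with Tukey" post hoc tests. The group-by-visit interaction is not mentioned.

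The section also compares the arms on baseline characteristics. That looks for imbalance but does not adjust any outcome for it. The document mentions no analysis of covariance or other baseline adjustment of an outcome.

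Methods describes a randomised trial with 20 treated and 10 untreated participants, and puts total cholesterol in the primary lipid profile alongside TG, HDL-C and LDL-C. Month 2 covers the whole treated arm: under the Secondary Aim, for instance, particle measurements are "performed in non-responders and responders at 2 months of treatment". Month 4 does not. A treated participant without a 25% TG improvement at month 2 "then he/she will be discontinued from the study drug under appropriate supervision and terminated from the study", and Primary Aim 2 says of month 4: "Lipid profiles will be performed in the drug responder and control groups".

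**The concern.** A 2 x 3 model yields three tests: group, visit and their interaction. The plan does not say which one answers whether fenofibrate changed the outcome, and the two it singles out answer other questions.

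In a randomised trial the expected difference between arms at baseline is zero. A group main effect taken over baseline, month 2 and month 4 therefore averages one visit with no effect and two with the effect. The time main effect averages over both arms and is not a treatment comparison. Tukey tests do not help: with two groups they add nothing to the group test, and on time they compare visits within the pooled sample.

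For VLDL-C, total cholesterol, glucose, insulin and the three ratios, no other group test is planned. What counts as a drug effect on these seven outcomes is left open until the output is seen.

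For TG, HDL-C and LDL-C, the percent-change ANOVA gives a valid, undiluted comparison at month 2. It uses baseline as a denominator but not as a covariate, which in a 30-person trial costs precision that could be kept at almost no cost.

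**Working it through.** **Inputs from the documents.** Allocation 20 to 10; significance level 0.05 (sidedness not stated, two-sided used here); visits baseline, month 2 and month 4. A 25% TG fall is the individual responder cut-off and serves here as a low-case mean effect. The Scientific Abstract reports that in monotherapy trials "serum TG concentrations fell 41-53" percent, so 41% serves as the second case.

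**Assumptions.** The documents give no SD, visit correlation, target effect or power, so there is no planned figure to reproduce. I assume a common SD σ, equal correlation ρ between visits (0.3, 0.5, 0.7), and log-TG SD of 0.35 or 0.45. For the RMANOVA I also assume an equal effect δ at months 2 and 4, and complete data.

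**1. Dilution of the group main effect (no SD or ρ needed).** The expected arm differences at the three visits are 0, δ, δ, with mean 2δ/3. For a 25% fall, δ = ln 0.75 = -0.288, and two thirds of it is -0.192. Since exp(-0.192) = 0.825, it reads as a 17.5% fall.

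**2. Variances per participant, in units of σ².**
- Mean of three visits: (1 + 2ρ)/3
- Change from baseline to month 2: 2(1 - ρ)
- Month 2 adjusted for baseline: 1 - ρ²

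The standard error of an arm difference is the square root of the variance times √(1/20 + 1/10) = 0.387. The ratio of adjusted to change variance is (1 + ρ)/2 = 0.65/0.75/0.85. Unadjusted change therefore needs 1.54/1.33/1.18 times as many participants.

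**3. An outcome tested only by RMANOVA, δ = 0.8 SD.** Worked at ρ = 0.5:
- Group main effect: 0.533 / (0.816 × 0.387) = 1.69; power 37% (28 df).
- Interaction: noncentrality (200/30) × (2/3) × 0.64 / 0.5 = 5.69 on F(2, 56); power 54%.
- Baseline-adjusted month 2: 0.8 / (0.866 × 0.387) = 2.39; power 63% (27 df).

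| Test | ρ = 0.3 | ρ = 0.5 | ρ = 0.7 |
|---|---|---|---|
| Group main effect | 45% | 37% | 32% |
| Interaction | 40% | 54% | 77% |
| Baseline-adjusted month 2 | 55% | 63% | 80% |

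The covariance formula runs 1 to 2 points high because it ignores estimation of the slope. The first two rows change order at a ρ of about 0.31 to 0.37, depending on effect size. Which term is read can therefore decide the conclusion.

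**4. TG at month 2 by simulation (40,000 runs).** Raw percent change compared between arms, against log TG adjusted for log baseline; power at ρ = 0.3/0.5/0.7:

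| True fall | Log SD | Percent change | Baseline-adjusted log TG |
|---|---|---|---|
| 25% | 0.35 | 42/54/76% | 55/64/80% |
| 25% | 0.45 | 28/37/55% | 38/44/59% |
| 41% | 0.35 | 88/96/99.8% | 97/99/99.9% |
| 41% | 0.45 | about 67/82/96% | about 84/91/98% |

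With no true effect, both tests reject about 5% of the time.

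**The case against.** **The interaction is in the model.** A two-factor repeated-measures ANOVA produces it as standard output, and the sentence on main effects is only a post hoc rule placed directly after the percent-change ANOVA, where a group effect is the right thing to read. This stands in part. A reader might infer that the plan makes the RMANOVA group main effect its test of the drug; the text does not say so. The two-thirds dilution is a consequence of one possible reading. What remains is that no term is designated and the only ones mentioned are unsuitable for this model.

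**TG is already covered.** This stands as to validity. A reader might infer that the efficacy analysis of TG is biased or has inflated error; at month 2 it is neither. The gain from adjustment is in precision, depends on an undocumented SD and ρ, and is small for a 41% fall at SD 0.35.

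**Chance baseline imbalance.** With 20 against 10, one standard error of baseline difference is 0.387 SD. This is ordinary sampling error already contained in the standard errors above, so it is not a separate argument.

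**Month 4.** A reader might also infer that the interaction would give false positives about half the time, because treated non-responders leave. In simulation (log SD 0.35, no true effect) it rejects 54 to 56% of the time if only participants with all three visits are analysed. But the plan states no complete-case rule, and its term mixed-model may mean a likelihood fit to all available data. On that reading the interaction rejects 5.0/6.8/4.7% (500 runs per setting). The documents do not settle which is meant, so the larger figure cannot be charged to the plan. Which model and estimand month 4 should have is a separate question.

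**Conclusion.** The point holds as a gap in specification and an avoidable loss of precision, not as an error that invalidates the trial. Two parts need no assumption about SD or correlation: no treatment contrast is named for the RMANOVA, and its group main effect would carry two thirds of a constant effect. The consequence is greatest for the seven outcomes with no other group test, of which total cholesterol belongs to the primary lipid profile.

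For TG, baseline adjustment at month 2 adds about 4 to 13 percentage points of power at a 25% fall and log SD 0.35. At a 41% fall it adds up to about 9 points at SD 0.35 and up to about 17 at SD 0.45, and close to nothing when ρ is 0.7. These sizes rest on assumed SDs and an equal correlation between visits. The ordering of the two month-2 methods does not depend on which ρ in the range is chosen. The change is worth making because it costs almost nothing.

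**What to change.** In the Statistical Analyses section:

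1. For each RMANOVA outcome, define the treatment effect as the between-arm difference at month 2, adjusted for that outcome's own baseline value. For TG, analyse on the log scale and report a percent difference with a 95% CI.
2. State that the RMANOVA group and time main effects will not be interpreted as treatment effects.
3. Keep percent change from baseline as a descriptive summary.
4. For month 4, state that observed treated data come from month-2 responders, so a contrast or interaction based on observed or complete cases only must not be read as a randomised treatment effect. Settle the month-4 model and estimand separately.

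The cost is SAP wording and about one error degree of freedom at month 2 (28 to 27). No new measurement is needed: Table 2 schedules lipids, fasting insulin and glucose at baseline and month 2, and Procedures confirms "determination of fasting plasma insulin level and serum glucose concentration at each study visit once the trial begins".

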outcome will be the lipoprotein particle number and size by NMR (i.e., HDL, LDL and VLDL subfractions). Liver (enzymes: AST, ALT, GGT) and kidney function (i.e., glomerular filtration rate) tests, and a complete blood count (CBC) with differential will be performed at all study visits, from blood samples, respectively, to monitor subject safety (Table 2). To facilitate our understanding of the relationship between metabolic parameters, body composition and primary study outcome measurements associated with treatment efficacy, a 2 hour oral glucose tolerance test, and a total body dual energy x-ray absorptiometry (DXA) scan will be performed to quantify total body fat mass and fat-free mass at baseline, as well as to determine visceral adipose tissue volume (enCore™ software (Lunar iDXA, platform version 13.6, General Electric Medical Systems, Madison, WI) at baseline and at 4 months. In addition, all subjects who enter the trial as a treatment or control subject will receive dietetic counseling at baseline and at 2 months. Study support staff will perform phone calls twice a month to monitor drug compliance and direct concerns to the study physician during intervals when there may be noncompliance with scheduled study follow-up visits. Thus, the proposed research investigation incorporates and follows best practices for the clinical treatment and utility of fenofibrate monotherapy in persons with dyslipidemia.

Table 2. Table of Procedures

	Screening	Baseline	Treatment				Follow-Up
			Month 1	Month 2	Month 3	Month 4	Post- 1 month
Safety Labs							
Liver and Kidney Function	x	x	x	x	x	x	x
CBC with Differential	x	x	x	x	x	x	x
Primary Study Outcomes							
Lipoprotein Concentrations	x	x	x	x	x	x	x
Lipoprotein Particle Number		x	x	x	x	x	x
Additional Outcomes							
Fasting Insulin, Glucose and A1	x	x	x	x	x	x	x
Oral Glucose Tolerance Test		x				x	
Body Composition Analysis		x				x	
ApoE blood genotyping		x					

Procedures

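### Inexpensive improvement at Month 2: the percent-change ANOVA names no baseline covariate, so a valid comparison is somewhat less precise than the collected data allow

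*Combined protocol and SAP*

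**What the plan says.** The Statistical Analyses section plans two between-group analyses of the lipids. The first is a repeated measures model: "Separate 2 (group: treatment, control) X 3 (visit: baseline, Mo2, Mo4) mixed-model repeated measures ANOVA (RMANOVA) will be performed". The second concerns TG, HDL-C and LDL-C: "factorial ANOVA will be performed to identify the presence of group differences in the percent change from baseline to 2 and 4 months". The factors of this factorial ANOVA are not listed and no covariate is named. In the repeated measures model, baseline is one level of the visit factor. Its group-by-visit test therefore compares changes and does not adjust for baseline.

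Baseline characteristics are only compared between arms: "Separate analysis of variance (ANOVA) will be performed to identify group differences (i.e., control, treatment) for baseline demographic data". Nothing is said about using the result.

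On allocation, Methods states that "Twenty subjects with adverse TG concentrations will be randomized to receive once daily fenofibrate therapy", with the remaining 10 as untreated controls. No stratification is described. Entry is by screening TG, with separate cut-offs for paraplegia (135 mg/dl) and tetraplegia (115 mg/dl). In Table 2 the row "Lipoprotein Concentrations" is marked at screening, baseline and every later visit.

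**The concern.** Dividing by baseline does not remove dependence on baseline. A subject whose baseline TG happens to be high tends to show a larger percent fall, with or without drug. If the arms differ in baseline TG by chance, the unadjusted difference in percent change moves with that imbalance. With 10 controls, sizeable imbalance is ordinary, and no stratification or model term limits its effect. Selection on screening TG also lowers the baseline to follow-up correlation among those enrolled, which makes adjustment more useful for TG.

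What is at stake is precision on the primary lipid outcome. Month 2 is the last visit before treated non-responders leave the study, so it is the cleaner of the two planned randomised comparisons. Naming the covariate in advance also avoids a choice between adjusted and unadjusted results after the imbalance has been seen.

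**Working it through.** **Inputs from the documents.** 20 treated and 10 controls (Methods); significance level 0.05 (Statistical Analyses; two-sided assumed); entry cut-offs 135 and 115 mg/dl (Inclusion Criteria). There is no SD, correlation, design effect or power figure to reproduce. A 25% fall is used for scale only. It is the individual responder cut-off in Primary Aim 1 ("a successful response will be defined as a 25% reduction in the serum TG concentration at 2 months"), not an expected mean effect. The only mean TG effects given are falls of 41-53%, in the Scientific Abstract.

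**Assumptions.** Log-normal TG with median 130 mg/dl, half with tetraplegia; log SD between persons 0.35 and within person 0.15, 0.20, 0.25 or 0.30; baseline drawn separately from screening. Uniform response means the same proportional effect in every treated subject. Varying response means individual log effects with SD 0.30. There were 20,000 simulated trials per setting.

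**Formula.** With correlation rho between baseline and Month 2:

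- change score: variance = 2(1 - rho) x SD² x (1/20 + 1/10)
- baseline-adjusted: variance = (1 - rho²) x SD² x (1/20 + 1/10) x (1 + 1/26)
- ratio = (1 + rho)/2 x 27/26

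At rho 0.5 the ratio is 0.75 x 1.038 = 0.78, and at 0.7 it is 0.85 x 1.038 = 0.88. That is like analysing 30/0.78 = 38 or 30/0.88 = 34 subjects in the planned way. At 0.9 the ratio is 0.99. Break-even is rho = 52/27 - 1 = 0.93.

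**Standard error at a 25% fall, covariate added on the percent scale.**

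| Within-person SD | rho after selection | Variance ratio (formula) | SE cut (formula) | SE cut, uniform (simulated) | SE cut, varying (simulated) |
|---|---|---|---|---|---|
| 0.15 | 0.73 | 0.90 | 5% | 5% | 2% |
| 0.20 | 0.63 | 0.85 | 8% | 8% | 5% |
| 0.25 | 0.55 | 0.80 | 10% | 10% | 7% |
| 0.30 | 0.47 | 0.76 | 13% | 12% | 9% |

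**Power at a 25% fall (%).**

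| Within-person SD | Planned, uniform | Percent change + covariate, uniform | Log ANCOVA, uniform | Planned, varying | Percent change + covariate, varying |
|---|---|---|---|---|---|
| 0.15 | 92 | 94 | 94 | 52 | 53 |
| 0.20 | 72 | 78 | 78 | 41 | 44 |
| 0.25 | 53 | 61 | 62 | 32 | 36 |
| 0.30 | 40 | 48 | 49 | 26 | 30 |

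At a 41% fall with uniform response, planned power is 100/99.6/95.6/86.5% and log ANCOVA gives 100/99.9/98.4/94.5%, a gain of 0 to 8 points. At 53% the gain is under 1 point.

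**Validity.** With no drug effect the planned test rejected in 4.8-5.1% of trials and log ANCOVA in 4.8-5.4%.

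**Imbalance.** At a 25% fall with uniform response, the planned estimate correlates with baseline imbalance at -0.35 to -0.48. Squared, that is 12-23% of its variance. With varying response the share is about 7-21%. For log ANCOVA the correlation is about 0. One SD of imbalance moves the planned difference by 2.8/4.5/6.6/8.4 points, within a standard error of 7.9/10.8/14.0/17.4 points.

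**Other lipids, assumed SDs.** At correlations 0.6/0.7/0.8/0.9, HDL-C (log SD 0.25, 20% rise) goes from 50/62/80/98% to 57/68/83/98% power with the covariate. LDL-C (log SD 0.30, 20% fall) goes from 56/68/84/98% to 62/73/86/99%. At a 6% LDL-C fall the gain is under 1 point.

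**Different assumptions.** With total log SD 0.45 and a single cut-off of 125 mg/dl, adding log baseline TG raised power at a 25% fall from 35% to 44%, 44% to 52%, 55% to 62% and 71% to 77% at pre-selection correlations 0.5, 0.6, 0.7 and 0.8.

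**The case against.** The strongest reply is that nothing here is an error. The Month 2 test holds its type I error, no statement in the documents is contradicted, and the choice is between two valid analyses. That stands, and it fixes the weight of the point. It also stands that every SD is assumed, and that the gain is small at the 41-53% falls the Scientific Abstract cites unless within-person noise is high or response varies. With varying response, much of the apparent advantage of log ANCOVA over the planned test comes from the change of scale and not from the covariate.

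It might be said that the unlisted factors already cover baseline. Nothing suggests this. ApoE genotype is collected to help stratify outcomes, but no model uses it, and it is not baseline lipid level.

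Three stronger readings are tempting and are not supported:

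- *The planned estimate is biased.* Trials with a baseline TG imbalance of 15% or more (22-38% of trials under these assumptions) give a planned difference off by about 5-12 points on average. That is conditional on the imbalance. Over all randomisations it is ordinary sampling error.
- *A confidence interval would be too narrow.* The plan specifies no interval, so there is nothing to fault.
- *Adjustment also rescues Month 4.* By then treated non-responders have been removed. With an inert drug and treated subjects showing less than a 25% fall dropped, the baseline-adjusted Month 4 estimate is still about -13%.

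**Conclusion.** The point holds as an inexpensive improvement, limited to Month 2. The planned comparison is valid but less precise than it need be. Part of its error, about 12-23% of variance with uniform response or 7-21% with varying response, can be removed with data already collected. The expected return is a standard error 5-12% smaller (2-9% if response varies). At a 25% fall that is 2-9 points of power with uniform response, or 1-4 points on the percent scale with varying response.

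These sizes rest on assumed SDs and on a correlation well below 0.9. The gain is 1-2 points at 0.8 and about nil near 0.9. The direction is secure over the plausible range; the size is not.

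**What to change.** For the Month 2 between-group comparison in all randomised subjects, pre-specify the baseline value of the same lipid as a covariate, with ordinary model standard errors. For TG, choose one of two forms in advance:

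- add log baseline TG to the planned percent-change ANOVA, which keeps the planned estimand; or
- use ANCOVA of log Month 2 TG on arm and log baseline TG, stating that it estimates a ratio of geometric means.

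Adjust HDL-C and LDL-C for their own baselines, and list the factors of the ANOVA in the same sentence. Keep the Aim 1 responder percentage as planned.

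The cost is a few sentences and one error degree of freedom (27/26, about 4% of variance, already counted above). The log form also changes the estimand: a 25% geometric-mean fall corresponds to a difference of 25.5-27.3 points in mean percent change with uniform response, and 22-23 points with varying response.

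Robust (HC3) standard errors should be a sensitivity analysis only. With percent change plus covariate and uniform response they give 90/69/50/36% power at a 25% fall, slightly below the planned test's 92/72/53/40%. No new data are needed. Month 4 needs its own solution.
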